9.1 Study Design

This will be a multinational, long-term, prospective observational cohort study using primary and secondary data collected by established international HSCT registries: the EBMT Registry and the CIBMTR Registry. The justification for leveraging these existing registries as key sources of data for this study is provided in Annex 1. The assessment of the registries is provided in Annex 2 (EBMT) and Annex 3 (CIBMTR).

The study will follow patients who received exa-cel for treatment of TDT or SCD following approval of the therapy in Germany, France, Italy, and UK (via EBMT) and US (via CIBMTR). The representativeness of the EBMT and CIBMTR Registries for transplant-eligible TDT and SCD populations in their respective regions is discussed in Section 9.2. Data on a broad range of safety and effectiveness outcomes, as well as important covariates, will be collected within EBMT and CIBMTR Registries via existing and custom, study-specific reporting forms.

The study enrollment period will continue for approximately 3 years following approval of exa-cel, with potential for enrollment expansion to up to 5 years if the target sample size is not reached (see Section 9.5). Eligible patients with TDT or SCD who are treated with exa-cel at the participating transplant centers reporting data to EBMT or CIBMTR and who consent to study participation will be included in TDT and SCD Exa-cel Cohorts. If any patients from participating centers receive exa-cel infusion prior to the study protocol approval, such patients will be considered for study inclusion. Included patients will be followed for up to 15 years after the administration of exa-cel. In addition, comparator populations of patients with TDT or SCD receiving an allo-HSCT within the participating transplant centers will also be followed for up to 15 years after transplant.

Measures to ensure long-term follow-up will include a combination of both transplant center and patient-specific interventions. In addition to standard patient-tracking routines, transplant centers participating in this sponsored study may receive additional education, patient tracking support, and/or tracking incentives based on annual patient follow-up.

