For each included exa-cel-treated and allo-HSCT-treated patient, data will be captured for the baseline pre-transplant period, immediate peri-transplant period (pre-transplant conditioning regimen, cell infusion / Day 0, first 100 days), 6 months after transplant and annually thereafter throughout the 15-year post-transplant period (see schedule of data collection in Section 9.3.6). Long-term safety and effectiveness outcomes among exa-cel recipients will be evaluated within the TDT and SCD Exa-cel Cohorts comparing the post-transplant period to the pre-transplant period, as appropriate. Comparison of the key outcomes to the allo-HSCT-treated comparator groups will also be performed. Findings will be discussed in the context of available literature on the natural history of TDT and SCD under the medical standard of care, as appropriate.

Analyses will be performed by each registry separately (EBMT: data from Germany, France, Italy, UK; CIBMTR: US). Furthermore, within each registry, analyses will be performed separately for the TDT and SCD populations. In addition to the separate analyses within each registry, pooled analyses of key safety outcomes (Section 9.3.3) are planned at pre-specified timepoints (after 5-, 10-, and 15-year duration of follow-up is accrued for all enrolled patients).

In addition, participating EBMT and CIBMTR transplant centers will be trained to collect and report directly to the Marketing Authorization Holder (MAH) information on all serious adverse events (SAEs), regardless of causality, among exa-cel recipients starting at the time of exa-cel infusion and throughout the course of the study. All SAEs reported by the centers for the exa-cel treated study participants (Section 11) will be summarized in the study progress reports, interim analysis reports, and final study report.

Should a hematologic malignancy be diagnosed among any patient receiving exa-cel, participating centers will be instructed to contact the MAH to report the event and determine appropriate samples for analysis (Section 12). The MAH will follow the testing strategies described in Section 12 to assess whether the malignancy developed as a result of off-target editing.

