9.5 Study Size

Exa-cel is an advanced therapeutic medicinal product targeted for individuals with 1 or more severe manifestations of rare hematologic disorders. HSCT for SCD and TDT is a rare procedure, with allogeneic transplants for SCD and TDT representing only a small fraction of the total annual HSCT volume managed by transplant centers. In 2019, hemoglobinopathies were only 1.4% of the HSCT volume reported to the EBMT¹⁵, and 1.1% of the reported volume in the US.^{16, 17} The average number of transplants performed historically (2016 through 2019) in Germany, France, Italy, UK, and US for patients with SCD and TDT who are 12 years of age and older without a matched donor (equivalent to the population indicated for exa-cel) is approximately 70 patients per year (CIBMTR data on file, EBMT data on file).¹⁶ It is expected that exa-cel will be available to only small numbers of patients in routine clinical practice.

As such, exa-cel enrollment targets include a minimum of 100 treated patients with TDT and 100 treated patients with SCD for a minimum of 200 exa-cel treated patients across all regions included in the study. It is expected that the enrollment period will be up to approximately 3 years, though may be extended to up to 5 years enrollment if the minimum sample size is not reached within 3 years.

It is anticipated that there will be an approximately equal number of allo-HSCT comparator patients enrolled. While eligibility for the Allo-HSCT Cohorts will be limited to patients aged 12 years and older, it will not be limited by donor type and may include patients from the larger pool of individuals receiving matched, mismatched or haploidentical donor transplants (see Section 9.1.2 for full inclusion / exclusion criteria).

Exa-cel uptake under real-world conditions is ultimately unknown and may be impacted by factors such as access and reimbursement, transplant center capacity to treat patients with newly available gene therapies, advances in allogeneic transplantation such as haploidentical transplant, potential availability of other gene or oral therapy products, and other unforeseen factors. Nevertheless, it is anticipated that approximately 1/3 of the final enrolled sample will be from European centers.

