9.7.1 Definition of Study Periods

For safety and effectiveness outcome analyses within the Exa-cel and Allo-HSCT Cohorts the pre-transplant and post-transplant periods will be defined as described below and illustrated in Figure 2:

- **Day 0 (transplant date)** is defined as the day of exa-cel product or allogeneic donor cell infusion, depending on cohort, as reported to the registries.
- **The pre-transplant / baseline period** will be broadly defined as the period prior to Day 0, with the length of the period varying depending on the study measures being evaluated:
 - For the *primary disease severity* measures (see Section 9.3.4 Effectiveness Outcome Variables) and *disease-related therapies* (see Section 9.3.5), the baseline period will be defined as 1 year prior to initiation of the conditioning regimen.
 - For *laboratory measures*, baseline will be defined as the non-missing measure most proximal, but prior to treatment initiation. This includes effectiveness measures such as total Hb, Hb fractionation (e.g., % HbS for SCD) and serum ferritin (see Section 9.3.4) as well other laboratory measures (see Section 9.3.5).
 - For pre-transplant *disease-related end-organ damage or dysfunction* (see Section 9.3.5) baseline will be defined as any time prior to the transplant.
 - Other variables such as patient demographics, pre-transplant height, weight and health status will be as reported at the most recent time point prior to transplant.
- The post-transplant period will continue for up to 15 years after the final enrolled patient's Day 0. For each patient, Year 1 will include events, new diagnoses or findings, and/or therapies initiated (or continued) within the first 365 days after Day 0; Year 2 will include the same occurring from patient day 366 to day 730, etc. Year 1 will further include the following time intervals based on existing transplant registry reporting: Day 0 to Day 100, Day 100 to 6 months, and 6-month to 1-year reporting. All patients, both exa-cel treated or comparator, will be followed for up to 15 years. Patients will be censored to last reported timepoint only after 2 years of loss to follow-up.

Figure 2 Study Periods

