9.7.5 Other Analyses

Additional key outcomes will also be evaluated for each cohort from each registry for each time point of the post-transplant period. Findings will be summarized as categorical or continuous measures, as appropriate:

• Post-transplant complications

- Post-transplant health status measures
- Post-transplant disease-related therapies
- Post-transplant additional laboratory measures, including relevant CBC results at each available timepoint throughout the study duration
- Post-transplant pregnancies

In addition to all analyses of the pre-specified outcome variables (Section 9.3.3 through 9.3.5) for both the exa-cel and allogeneic HSCT cohorts, Serious Adverse Events (SAEs) among participating exa-cel recipients reported to the sponsor per Section 11 will be provided with each study report as a summary tabulation (proportion of exa-cel treated patients with SAE reports, by type) and in a listing format. Findings from the hematologic malignancy evaluation (Section 12) will also be provided, where available.

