11.1 Definitions

• Adverse Event

An AE is defined as any untoward medical occurrence in a subject during the study; the event does not necessarily have a causal relationship with the treatment. This includes any newly occurring event or previous condition that has increased in severity or frequency. A subset of AEs may meet serious criteria.

Planned hospital admissions or surgical procedures for an illness or disease that existed before the subject was screened in the study are not to be considered AEs unless the condition deteriorated in an unexpected manner during the study (e.g., surgery was performed earlier than planned).

• Serious Adverse Event

An SAE is any AE that meets any of the following criteria:

- Results in death
- Life-threatening
- Requires hospitalization or prolongation of existing hospitalization
- Results in persistent or significant disability / incapacity (substantial disruption of the ability to conduct normal life functions)
- Congenital anomaly or birth defect
- Important medical event that, based upon appropriate medical judgment, may jeopardize the subject or may require medical or surgical intervention to prevent 1 of the outcomes listed above (e.g., a new hematologic malignancy diagnosis).

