11.3 SAE Reporting Procedure

All SAEs observed in patients exposed to exa-cel accessed via commercial availability, regardless of the presumed relationship to any Vertex medication exposure, must be reported to

the MAH using the Non-interventional (NI) Study Safety Information Collection Form (study number must be included on the form).

Any hematologic malignancy diagnosis is considered an important medical event that must be reported to the MAH following SAE reporting guidance.

This reporting is required from the time informed consent and assent, where applicable, is signed and while the patient is participating in the study, for all SAEs that occur at any time after exa-cel infusion. Complete and comprehensive case information must be documented and causality assessments performed.

Reportable SAEs should be reported by the HCP to the MAH **within 24 hours** of awareness. NI Study Safety Information Collection Forms should be submitted to:

Vertex Global Patient Safety

Email: [contact] (*preferred*) Or via [contact] For questions, contact [contact]

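### The SAE table fixed in 9.7.5 has no time axis, so repeat late events of types common around transplant are diluted in the summary

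*Protocol*

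**What the plan says.** Section 9.7.5 of the protocol says that every study report will give SAEs as a "summary tabulation (proportion of exa-cel treated patients with SAE reports, by type) and in a listing format". The statistic is a proportion of treated patients. The sentence names no time window, event count, person-time or time to onset, and does not say what the listing contains.

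The collection window is long. Section 9.1 has SAEs reported "among exa-cel recipients starting at the time of exa-cel infusion and throughout the course of the study", and Section 11.3 requires reporting "for all SAEs that occur at any time after exa-cel infusion". Section 9.1 also states: "Included patients will be followed for up to 15 years after the administration of exa-cel". The SAEs "will be summarized in the study progress reports, interim analysis reports, and final study report". The seriousness criteria in Section 11.1 include "Requires hospitalization or prolongation of existing hospitalization".

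The protocol already has a time grid. Section 9.7.1 divides follow-up into years and splits Year 1 into "Day 0 to Day 100, Day 100 to 6 months, and 6-month to 1-year reporting". Section 9.7.3 (safety), Section 9.7.4 (effectiveness) and the first part of Section 9.7.5 (additional outcomes) all report by timepoint or follow-up period. The SAE sentence does not.

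Table 2 schedules transplant-related complications, which Section 9.3.5 says include infection and bleeding, at Day 100, Month 6 and Year 1 only. The target in Section 9.5 is "a minimum of 100 treated patients with TDT and 100 treated patients with SCD for a minimum of 200 exa-cel treated patients".

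**The concern.** The weeks after infusion and the following years are very different risk periods. A patient who is in hospital for transplant can easily meet the criterion of prolonged hospitalization. If one proportion covers both periods, a patient with an early infection SAE is counted once, and an infection SAE in Year 6 adds nothing to the table.

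Three features of this study make the missing time axis matter:

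- SAEs are collected for exa-cel recipients only. With no allo-HSCT comparator, time since infusion is the main contrast that the SAE data offer, and the stated table removes it.
- Infection and bleeding have no scheduled item as transplant complications after Year 1, so serious late cases reach the study mainly through SAE reports. Hemorrhagic stroke is an exception: it is collected yearly as end-organ damage.
- The denominator is treated patients, while Section 9.9.5 expects loss to follow-up that may be differential. Without person-time, a late risk is understated as follow-up thins.

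**Working it through.** The protocol states no SAE rate and no calculation on SAEs, so there is no figure of its own to reproduce. The check shows how a cumulative ever/never proportion responds to late events.

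**Inputs**

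- n = 100 per disease, 200 in total (Section 9.5).
- p1 = proportion with an SAE of a given type around transplant. Not in the protocol; assumed 0% to 90%.
- p2 = proportion with a late SAE of the same type. Not in the protocol; assumed 10%, with 5% and 20% as a range.
- Early and late events independent; no attrition; table cumulative from infusion.

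**Formulae**

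- Ever-proportion = 1 - (1 - p1)(1 - p2).
- Rise caused by late events = (1 - p1) × p2, so the share of the late signal that stays visible is 1 - p1.

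**Results for n = 100, p2 = 10%** (exact Clopper-Pearson 95% intervals)

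| p1 | Early only | Ever (early or late) | Of 10 late patients, new in table |
|---|---|---|---|
| 0% | 0% | 10% (4.9 to 17.6) | 10 |
| 10% | 10% (4.9 to 17.6) | 19% (11.8 to 28.1) | 9 |
| 30% | 30% (21.2 to 40.0) | 37% (27.6 to 47.2) | 7 |
| 60% | 60% (49.7 to 69.7) | 64% (53.8 to 73.4) | 4 |
| 90% | 90% (82.4 to 95.1) | 91% (83.6 to 95.8) | 1 |

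Example, last row: 1 - 0.10 × 0.90 = 0.91, a rise of 0.10 × 0.10 = 1 point.

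**Range of p2.** At p1 = 90% the rise is 0.10 × 0.05 = 0.5 points for p2 = 5% and 0.10 × 0.20 = 2 points for p2 = 20%. At p1 = 10% it is 0.90 × 0.05 = 4.5 and 0.90 × 0.20 = 18 points.

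**Independence.** In general the rise is p2 times the probability that a patient with a late event had no early one. If the same patients tend to have both, dilution is stronger than in the table; if different patients do, it is weaker.

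**With a period-specific table.** The same late risk shows as 10/100 = 10% (4.9 to 17.6), or 20/200 = 10% (6.2 to 15.0), whatever p1 is. If late means Years 2 to 15 and each of the 10 patients has one event, the rate is 10 / (100 × 14) person-years = 0.71 per 100 person-years. With attrition, the denominators would be the patients and person-time still under follow-up.

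**Unequal periods.** The first 100 days are 100 / (15 × 365.25) = 1.8% of a 15-year follow-up, yet they can fix a patient's status in the table for the rest of the study.

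**The case against.** The best counter-argument is that this is table layout. Section 9.7 leaves further detail to the SAP, which is not shown, and nothing in Section 9.7.5 forbids columns by period. That stands in part: the SAP may already split the table. But the protocol does not leave the measure open. It names one for SAEs without a time axis, while the outcomes around it are reported by timepoint.

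A reader might also infer more than the text supports:

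- *Late harm cannot show.* The same sentence promises a listing, and about 200 patients can be read case by case. Types rare early keep at least 90% of the late signal when p1 is 10% or less. But a listing gives no rate or denominator, and its fields are not stated.
- *Early events saturate the table.* No SAE rate is given, and finer coding of type lowers each early proportion.
- *SAEs are the only late safety channel.* Section 9.7.3 reports malignancy, hematologic disorder and death by timepoint, with cumulative incidence or overall survival. Table 2 continues end-organ damage and laboratory measures to Year 15. Section 9.3.3 ties the primary objective to its listed outcomes, and SAEs are not among them.
- *Successive reports cannot be compared because the proportion only rises.* During enrollment the denominator grows, so it can fall. After enrollment, differencing successive tables gives newly affected patients, but still misses repeat events in patients already counted.

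Section 9.7.5 also does not say that each table is cumulative. A table per reporting interval would dilute less, but would mix patients at different times since infusion.

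**Conclusion.** The concern holds in a limited form. The SAE measure fixed in Section 9.7.5 has no post-transplant period, event count or person-time over a window of up to 15 years. For types common around transplant, repeat late events are diluted in the summary by (1 - early proportion) and can be seen, at best, in the listing. Infection and bleeding are the clearest candidates because of the Year 1 cut-off in Table 2.

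The size depends on the type. With an assumed late risk of 10%, the visible rise is 1 point at an early proportion of 90%, 4 points at 60% and 9 points at 10%. This rests on assumed rates, independence, no attrition and a cumulative table. The documents do not show that late harm in general would be hidden, and the main late outcomes have their own analyses by timepoint. This is a reporting weakness that should be corrected. It is not a contradiction or a wrong figure.

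**What to change.** In Section 9.7.5, tabulate SAEs by type within the periods of Section 9.7.1: Day 0 to 100, Day 100 to 6 months, 6 months to 1 year, then each year. For each period give:

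- patients with at least one SAE, out of those under follow-up in that period;
- number of events;
- events per 100 person-years.

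Count a patient again in each later period in which an SAE occurs. Keep the overall proportion as one column, and state that it is cumulative from infusion. Include SAE onset, in days from Day 0, in the listing.

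The main cost is a longer table. No extra patients or visits are needed. Day 0 and date of last follow-up are registry variables already (Sections 9.3.2 and 9.3.3). Two points need confirming. The SAE form is not shown, so collection of onset date is a reasonable inference from the complete case information required in Section 11.3, but it is not stated. SAEs go to the sponsor while follow-up dates sit in the registries, so the registries must supply the denominators or the pseudonymized patient-level data mentioned in Section 9.7.

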9.8 Quality Control

9.8.1 EBMT

The EBMT's quality control system relies primarily upon electronic data entry control triggers that promote consistency of the data and data quality / completion reports provided to the individual transplant centers. Data quality and completion reports may include information on percent of patients with annual reporting as well as individual missing data and statistical assessments for outlying data points. The EBMT provides assistance (e.g., completion guidelines per data collection form, training modules, help desk support) for form completion. Although there is no external audit system of the EBMT Registry, the present study the contractual agreement with the EBMT Registry will include the remote and/or on-site monitoring and source data verification of 10% of all patients enrolled in the study with the costs charged to the sponsor.

Primary data collection for this study implies ethics committee procedures to have Informed Consent Forms in place with the option to share the data with the sponsor.

With study-specific funding to the EBMT, processes to ensure higher data quality and completeness will be implemented. Additional site personnel training will be applied by the EBMT with dedicated clinical study unit personnel. These specialists may be recruited specifically to support the study and their costs will be charged to the sponsor.

Furthermore, to facilitate the completeness of the data in the present study a documentation fee will be provided to the participating centers, which will be reduced when the data provided is significantly incomplete or of poor quality. Data completeness will need to be maintained at the 80% level or higher to receive the full documentation fee.

For sponsored studies the EBMT is planning to have a third party audit every 2 to 3 years.

9.8.2 CIBMTR

The CIBMTR enacts a range of automatic and in-person procedures to ensure data quality and complete reporting from the associated transplant centers. Data submitted electronically through the FormsNet system (including data collected by study-specific / supplemental forms) is automatically checked for consistency of patient data across individual forms, validation of the

numeric information entered, and mandatory field entry for core questions. Centers are queried with follow-up until resolution of inconsistent data fields.

The CIBMTR monitors form completion, data verification, and IRB documentation according to its continuous process improvement (CPI) standards. To maintain CPI compliance, a center must submit at least 98% of pre-transplant essential data, 100% of supplemental study data, and >95% of all other data due each trimester to maintain "good standing" for CPI. Throughout the 15-year post-gene therapy timeframe, form submission will be monitored on a regular basis with follow-up with centers that are not submitting forms in a timely manner.

In addition, CIBMTR transplant centers are audited every 4 years to assure appropriate and quality procedures are in place. All data elements on all forms are subject to audit. However, the audit concentrates on "critical" data, i.e., data most likely to be included in a research study. Data elements considered "non-critical" are randomly audited to increase the validity of the audit error rates. An average of 10,000 fields are reviewed per audit. Any center's audit(s) resulting in a critical field error rate of >3% for 2 consecutive audits results in audit consequences.

